### 10.5.2 Modified Intent to treat (mITT)

The mITT analysis population includes all randomized subjects who received at least one injection of IC2000 or Blue dye. All subjects meeting this criterion are included in the mITT population regardless of whether or not they received the minimally invasive surgical intervention or lymphatic mapping. Subjects who have the mapping procedure aborted due to circumstances such as a higher stage cancer than initially expected will not be included in the mITT. Approximately 8% of subjects are expected to have the mapping procedure aborted.

We believe the mITT population will be the population that will most likely demonstrate no difference between the Blue dye and IC2000 with respect to their ability to identify lymph nodes, because the mITT population includes subjects who may not have received the full dose of dye, and it includes subjects who may have not received lymphatic mapping, but who may have had lymph nodes identified by gross inspection. Thus, we believe that using the mITT population for testing superiority will be the conservative approach.

### 10.5.3 As-Treated (AT)

The As-Treated (AT) analysis population includes all randomized subjects in whom the intended minimally invasive surgical procedure was performed and received at least one injection of IC2000 or Blue dye. Subjects in whom the mapping procedure with PINPOINT or Blue dye is not performed are excluded from the AT population. Subjects will be analyzed according to the LN mapping procedure performed. The AT population will be used for a secondary analysis of the primary endpoint.

### 10.5.4 Safety (S)

The safety analysis population includes all randomized subjects enrolled in the study who received at least one injection of IC2000 or Blue dye. Secondary safety endpoints, including the summary of adverse events or adverse device effects in the trial, will be analyzed using this analysis population.

## 10.6 Secondary Objectives

The planned secondary outcomes are intended to support product labelling. We will use the step-down method described by Benjamini and Liu to control the false discovery rate at 0.05 (2-sided) while testing our secondary objectives.

The first secondary outcome is the ability of PINPOINT and Blue dye to detect at least one lymph node in a subject.

Let  $q_t$  and  $q_c$  represent the proportion of subjects with at least one lymph node identified (according to [section 8.3.1.5](#) and confirmed by histology) with PINPOINT and Blue dye respectively, divided by the total number of subjects where mapping was attempted. That is, the numerator for  $q_t$  is the number of subjects with at least 1 node identified with PINPOINT (classifications 1, 3, 5, 7) and confirmed as lymphoid tissue, and the numerator for  $q_c$  is the number of subjects with at least 1 node identified with Blue dye (classifications 2, 3, 6, 7) and confirmed as lymphoid tissue. The denominator of both  $q_t$  and  $q_c$  is the number of subjects where mapping was attempted.

The following hypotheses will be tested:

$$\begin{aligned} H_{03}: q_t &\leq q_c - 0.05 \\ H_{13}: q_t &> q_c - 0.05 \end{aligned}$$

To test this hypothesis we will estimate the difference  $q_t - q_c$  with a 95% two-sided confidence interval. We will perform this analysis using the PP analysis set to test the inferiority hypothesis ( $H_{03}$ ) stated above, and if the lower bound of the interval is greater than -0.05 we will claim non-inferiority. If and only if we reject the inferiority hypothesis ( $H_{03}$ ) we will use the mITT analysis set to test for superiority, and if the lower bound of the interval is greater than 0 we will claim superiority.

Another secondary outcome is the bilateral LN detection rate. Let  $b_t$  and  $b_c$  represent the proportion of subjects with at least one node identified on the right side and on the left side of the pelvis and confirmed as lymphoid tissue with PINPOINT and Blue dye, respectively. That is, the numerator for  $b_t$  is the number of subjects with at least 1 node identified with PINPOINT () on the right side of the pelvis and confirmed as lymphoid tissue and at least 1 node identified with PINPOINT on the left side of the pelvis and confirmed as lymphoid tissue. Similarly, the numerator for  $b_c$  is the number of subjects with at least 1 node identified with Blue dye (classifications 2, 3, 6, 7) on the right side of the pelvis and confirmed as lymphoid tissue and at least 1 node identified with Blue dye on the left side of the pelvis and confirmed as lymphoid tissue. The denominator of both  $b_t$  and  $b_c$  is the number of subjects where mapping was attempted.

The following hypotheses will be tested:

$$\begin{aligned} H_{04}: b_t &\leq b_c - 0.05 \\ H_{14}: b_t &> b_c - 0.05 \end{aligned}$$

To test this hypothesis we will estimate the difference  $b_t - b_c$  with a 95% two-sided confidence interval. We will perform this analysis using the PP analysis set to test the inferiority hypothesis ( $H_{04}$ ) stated above, and if the lower bound of the interval is greater than -0.05 we will claim non-inferiority. If and only if we reject the inferiority hypothesis ( $H_{04}$ ) we will use the mITT analysis

set to test for superiority, and if the lower bound of the interval is greater than 0 we will claim superiority.

A third secondary outcome is the proportion of LNs identified by following lymphatic channels (ducts). Let  $d_t$  and  $d_c$  represent the proportion of nodes identified by following a duct and confirmed as lymphoid tissue with PINPOINT and Blue dye, respectively. That is, the numerator for  $d_t$  is the number of nodes identified with PINPOINT by following a duct (classifications 5, 7) and confirmed as lymphoid tissue. Similarly, the numerator for  $d_c$  is the number nodes identified with Blue dye by following a duct (classifications 6, 7) and confirmed as lymphoid tissue. We define the denominator for both  $d_t$  and  $d_c$  as the number of nodes identified by ANY method (classifications 1-7). The denominator will include excised nodes confirmed as lymphoid tissue.

The following hypotheses will be tested:

$$\begin{aligned} H_{05}: d_t &\leq d_c - 0.05 \\ H_{15}: d_t &> d_c - 0.05 \end{aligned}$$

To test this hypothesis we will estimate the difference  $d_t - d_c$  with a 95% two-sided confidence interval. We will estimate this confidence interval in a manner similar to that described for the primary outcome. We will perform this analysis using the PP analysis set to test the inferiority hypothesis ( $H_{05}$ ) stated above, and if the lower bound of the interval is greater than -0.05 we will claim non-inferiority. If and only if we reject the inferiority hypothesis ( $H_{05}$ ) we will use the mITT analysis set to test for superiority, and if the lower bound of the interval is greater than 0 we will claim superiority.

We will also tabulate the anatomic distribution of LNs identified by each dye.

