**Other Variables**

- Bilateral LN detection rate defined as the proportion of cases in which at least one LN is identified on right and left side of the pelvis.
- Proportion of LNs identified from following LCs.
- Anatomic distribution of LNs.

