***Sample Size and Statistical Analysis:***

The FILM trial is a non-inferiority study comparing lymph node detection rates between Blue dye and PINPOINT. A sample size of approximately 150 evaluable subjects (to identify 525 LNs) is required to show the LN detection rate for PINPOINT is non-inferior to that with Blue dye with 80% power and a 5% 2-sided significance level with a 5% non-inferiority margin.

Both a modified Intent-to-Treat (mITT) and Per-Protocol (PP) analysis population will be utilized for the primary analysis. Analysis of the primary objective will be conducted using a 2-sided 95% confidence interval for the difference in proportions. A non-inferiority test will be conducted using the PP and the mITT analysis populations. If and only if non-inferiority is claimed, a superiority test will be conducted using the mITT analysis population. As a supporting analysis of the primary outcome, the analysis will also be repeated using the as-treated (AT) population. The secondary objectives will be tested using a two-sided 5% significance level with a step-down multiplicity adjustment.

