#### **2.1.2 Secondary Objectives**

- To evaluate the effectiveness of PINPOINT and Blue dye in the identification of at least one LN (confirmed to be lymphoid tissue) per subject.
- To evaluate the effectiveness of PINPOINT and Blue dye in the identification of bilateral LNs (confirmed to be lymphoid tissue).
- To assess the safety of interstitial injection of ICG for intraoperative lymphatic mapping.
- To determine the proportion of LNs identified from following LCs.
- To find the anatomic distribution of LNs.

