A non-inferiority margin of 0.05 was determined to be clinically significant based on feedback from Investigators. Within their respective groups, p_t and p_c represent the proportion of LNs identified (and confirmed to be lymphoid tissue) with PINPOINT and Blue dye respectively divided by the total number of LNs identified and excised, across all subjects.

We will use the Z_0 statistic described by Nam and Kwon (Nam J-M and Kwon D. Non-inferiority tests for clustered matched-pair data. *Statistics in Medicine*. 2009(28):1668-1679) in formulae (6) to derive the estimates of p_t , p_c , and the variance of the difference between these estimates to construct the 95% 2-sided confidence interval for $p_t - p_c$ as:

$$\left((\hat{p}_t - \hat{p}_c) - 1.96 \times \sqrt{\widehat{var}(\hat{p}_t - \hat{p}_c)} , (\hat{p}_t - \hat{p}_c) + 1.96 \times \sqrt{\widehat{var}(\hat{p}_t - \hat{p}_c)} \right)$$

We will perform this analysis using the PP analysis set to test the inferiority hypothesis (H_{01}) stated above, and if the lower bound of the interval is > -0.05 we will claim non-inferiority. If and only if we reject the null (H_{01}) hypothesis of inferiority and claim non-inferiority we will use the mITT analysis set to test the null hypothesis (H_{02}) stated below, and if the lower bound of the interval is > 0 we will claim superiority.

$$H_{02}: p_t = p_c$$

$$H_{12}: p_t > p_c$$

We will repeat the analysis described above using the as-treated (AT) analysis set as a supporting analysis of the primary outcome.

As a sensitivity analysis we will also perform the non-inferiority test using the mITT analysis set. We will also perform sensitivity analyses of the primary endpoint using a best-case and a worst-case scenario. The best-case scenario will consider nodes with missing histology to be lymphoid tissue for PINPOINT and non-lymphoid tissue for Blue dye. The worst case scenario will consider nodes with missing histology to be non-lymphoid tissue for PINPOINT and lymphoid tissue for Blue dye.

Secondary Efficacy Outcomes

The planned secondary outcomes are intended to support product labelling. We will use the step-down method described by Benjamini and Liu (Benjamini Y, Liu W. A step-down multiple hypothesis testing procedure that controls the false discovery rate under independence. *Journal of Statistical Planning and Inference*. 1999(82):163-170) to control the false discovery rate at 0.05 (2-sided) while testing our secondary objectives.

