The first secondary outcome is the ability of PINPOINT and Blue dye to detect at least one lymph node in a subject. Let q_t and q_c represent the proportion of subjects with a least one node identified and confirmed as lymphoid tissue with PINPOINT and Blue dye respectively, divided by the total number of subjects where mapping was attempted. That is, the numerator for q_t is the number of subjects with at least 1 node identified with PINPOINT (PINPOINT alone, both Blue dye and PINPOINT, non-stained node found at termination of Fluorescent duct, Blue-stained node found at termination of a Fluorescent duct, non-stained node found at termination of duct stained with both Blue dye and Fluorescent dye) and confirmed as lymphoid tissue, and the numerator for q_c is the number of subjects with at least 1 node identified with Blue dye (Blue dye alone, both Blue dye and PINPOINT, non-stained node found at termination of Blue duct, Fluorescent-stained node found at termination of Blue duct, non-stained node found at termination of duct stained with both Blue dye and Fluorescent dye) and confirmed as lymphoid tissue. The denominator of both q_t and q_c is the number of subjects where mapping was attempted.

Table 4 summarizes the data to address this secondary objective.

Table 4. Number of Subjects with ≥ 1 Lymph Node Identified						
Identification Method	B-P Arm		P-B Arm		Total	
	N	%	N	%	N	%
PINPOINT						
Blue Dye						
Number of Subjects						

We will test the following hypotheses:

$$H_{03}: q_t \leq q_c - 0.05$$

$$H_{13}: q_t > q_c - 0.05$$

To test this hypothesis we will estimate the difference $q_t - q_c$ with a 95% two-sided confidence interval. We will perform this analysis using the PP analysis set to test the inferiority hypothesis (H_{03}) stated above, and if the lower bound of the interval is > -0.05 we will claim non-inferiority. If and only if we reject the inferiority hypothesis (H_{03}) we will use the mITT analysis set to test for superiority, and if the lower bound of the interval is > 0 we will claim superiority.

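### The labelling-support secondary outcomes (H03 to H05) have two decision rules that are not tied together, and no gate on the primary result

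*Protocol*

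**What the plan says.** Protocol 10.6 states the purpose of these outcomes: "The planned secondary outcomes are intended to support product labelling". It names a Benjamini-Liu step-down to "control the false discovery rate at 0.05 (2-sided) while testing our secondary objectives". The SAP, under Secondary Efficacy Outcomes, names the same method "to control the false discovery rate at 0.05 (2-sided) while testing our secondary objectives". The Protocol Summary puts it more generally: "The secondary objectives will be tested using a two-sided 5% significance level with a step-down multiplicity adjustment".

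The same sections then give H03 (at least one node per subject), H04 (bilateral detection) and H05 (nodes found by following a duct) a complete rule each. The difference is estimated with a two-sided 95% interval in the per-protocol set, and "if the lower bound of the interval is greater than -0.05 we will claim non-inferiority". The SAP repeats this: "if the lower bound of the interval is > -0.05 we will claim non-inferiority". If non-inferiority is shown, superiority is claimed for that outcome when the mITT interval lies above 0.

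The only gate from the primary analysis (Protocol 10.3 and the SAP) runs from primary non-inferiority, H01, to primary superiority, H02.

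**The concern.** Each rule is complete without the other. The documents define no p-value for the step-down and do not adjust the level of any interval. They do not say whether one rule or both must be met, or whether the family has three tests or six with superiority. Nor do they make H03 to H05 wait for H01. Two analysts could each follow written text and report different label claims from the same data. The rule written directly under each hypothesis is also the one that does not, by itself, deliver the promised false discovery rate (FDR).

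**Working it through.** **Inputs.** From the documents: FDR 0.05 two-sided; three secondary non-inferiority tests; 95% intervals with margin 0.05. Claiming when the lower limit exceeds -0.05 amounts to a one-sided 0.025 test. Assumed, because the documents name the method without printing its constants: thresholds d_i = 1 - [1 - min(1, mq/(m-i+1))]^(1/(m-i+1)), with m = 3 and q = 0.05. True nulls are placed at the margin, the worst case.

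**1. The plan's own figure.** The thresholds on ordered two-sided p-values are 0.01695, 0.03823 and 0.15. With three independent true nulls, 1 - (1 - 0.01695)^3 = 0.0500, which matches the promised FDR.

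**2. Interval rule alone: chance of at least one false claim in PINPOINT's favour.**
- Three true nulls: 1 - 0.975^3 = 7.3%. With equally correlated normal statistics it is 6.3% at correlation 0.5, 5.5% at 0.7 and about 4.9% at 0.8. With all nulls true, every claim is false, so this is also the FDR.
- Two true nulls: 1 - 0.975^2 = 4.9%. If the third outcome is clearly rejected, the FDR is 2(0.025)(0.975)(1/2) + 0.025^2(2/3) = 2.5%.
- One true null beside two clear rejections: FDR = 0.025/3 = 0.8%.

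**3. Step-down alone and both rules together.** Simulation with 2,000,000 replicates, independent statistics, real effects shifted by 6 standard errors, and only claims in PINPOINT's favour counted:

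| True nulls | Interval rule | Step-down | Both required |
|---|---|---|---|
| 3 | 7.3% | 2.6% | 2.6% |
| 2 | 4.9% | 4.0% | 3.8% |
| 1 | 2.5% | 7.5% | 2.5% |

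The closed form for the step-down, 1 - (1 - d/2)^k, gives 2.5%, 3.8% and 7.5%. The simulation is slightly higher because a rejection in the unfavourable direction also lets the procedure move on. With both rules required, the FDR is at most about 2.6%.

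**4. Sensitivity to the assumed constants.** The distribution-free thresholds mq/(m-i+1)^2 are 0.01667, 0.0375 and 0.15. They give 2.5%, 3.7% and 2.5% when both rules are required. If one-sided p-values were used at q = 0.05, both rules would allow 5.0%. If the family were six tests, the fourth threshold would be 1 - 0.9^(1/3) = 0.0345. Three true superiority nulls, reached after all three non-inferiority rejections, would then allow 1 - (1 - 0.01726)^3 = 5.1% even with both rules. The p-value and the family therefore have to be defined.

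**5. Neither rule contains the other.** Take two-sided p-values against the margin, all in PINPOINT's favour.
- 0.02, 0.03, 0.04: three claims by interval; none by step-down, because 0.02 > 0.01695.
- 0.001, 0.01, 0.10: two claims by interval; three by step-down, the third with a 95% interval that crosses -0.05.

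Across correlations 0 to 0.7, the claim sets differ in 21-26% of trials at 80% power per test and in 13-17% at 90%.

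**6. No gate.** If the primary null is also true, the interval rule gives at least one false claim among the four in 1 - 0.975^4 = 9.6% (7.8% at correlation 0.5). With a gate on H01, the figure cannot exceed 2.5%.

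**The case against.** The strongest reply is that the step-down sentence opens the secondary section and governs everything beneath it, so an analyst who used the intervals alone would be ignoring it. That is a reasonable reading, and under it the 7.3% does not arise. But no sentence says so. If the step-down governs alone, it can also claim non-inferiority when the interval crosses -0.05, contrary to the rule written under each hypothesis.

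Several stronger conclusions might be inferred, and the documents do not support them:

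- **That the promised FDR is broken in general.** It is missed only when all three nulls are true and, read literally as 5%, only at correlations below about 0.8. H05 can be a true null only if the Blue-dye duct proportion is at least 5%, a figure the documents do not give.
- **That the error is 14.3%.** The figure 1 - 0.95^3 counts rejections against PINPOINT, which no rule turns into a claim.
- **That the plan exceeds a stated 2.5% familywise limit.** No such limit is set for the secondary outcomes; 2.5% is only the one-sided half of the stated 5%.
- **That FDR control must be abandoned.** It is a legitimate choice, and requiring both rules keeps it.

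The practical effect may also be small. With 150 subjects and pairing ignored, power is Φ[(difference + 0.05)/SE - z]. The prospective three-tracer comparison in Protocol 1.1.4 reports 87% vs 71% unilateral and 65% vs 43% bilateral detection. At those rates the 95% interval passes in 99.5% and 99.8% of trials, and the strictest step-down threshold in 98.5% and 99.2%. At the weighted averages in Protocol 10.4 (91% vs 80%) the figures are 97.9% and 94.5%. The rules separate at the cautious 84% vs 80% planning rates: SE = √(0.2944/150) = 0.0443, giving 53% and 36%. Those rates were chosen for the node-level primary, so their use for a subject-level outcome is illustrative.

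**Conclusion.** The point holds as a conflict between two written decision rules for labelling claims, together with a missing gate. It should be fixed before the data are analysed. The absence of a link between the rules and the absence of a gate can be read directly from the text. So can the interval-rule figures, given the stated correlation. The step-down figures, the 3.8% maximum and the 13-26% disagreement rest on the method's standard constants and a three-test family, neither of which the documents state. The excess error is modest if both rules are required. A reader might infer that the primary non-inferiority or superiority claim is also weakened; it is not, because H01 and H02 have their own rule and their own gate.

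**What to change.** In Protocol 10.6 and the SAP, state that:

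1. secondary claims are made only if primary non-inferiority (H01) is met;
2. a secondary non-inferiority or superiority claim requires both rejection by the step-down and a 95% lower limit above -0.05 or 0 respectively, with the family named, the two-sided p-values defined and the thresholds printed.

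If the sponsor wants familywise control for labelling, there are two acceptable options. One is a pre-fixed sequence at the 95% level after the primary; the other is Holm with matching interval levels.

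**Cost.** No extra subjects, but some secondary power, and no secondary claim if the primary fails. In the simulation above, with three equally powered non-inferiority tests and correlation 0 to 0.7, requiring both rules lowers average power per test from 90% to 87-89% and from 80% to 75-77%. With 90% power per test, a fixed sequence lowers the second test to 81-85% and the third to 73-81%. Holm lowers each of the three to 86-88%.

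One editorial change goes with this. Section 2.1.2 lists bilateral detection as a secondary objective ("To evaluate the effectiveness of PINPOINT and Blue dye in the identification of bilateral LNs (confirmed to be lymphoid tissue"), as it does the duct outcome. The Protocol Summary places both under Other Variables (for example "Bilateral LN detection rate defined as the proportion of cases in which at least one LN is identified on right and left side"). The summary should be aligned with 2.1.2, 10.6 and the SAP.

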### 10.6.1 Demographic and Baseline Data

The demographic and baseline analysis will be done for the mITT and PP data set.

The following subject variables will be summarized: age, race, body mass index, histological type (squamous cell carcinoma, adenocarcinoma, endometrioid carcinoma etc.), previous neoadjuvant therapy, FIGO stage and type of surgical intervention. Continuous variables will be summarized as mean, standard deviation, median, minimum and maximum, and categorical variables will be summarized by counts and percentages.

### 10.6.2 Safety Variables and Analysis

Safety variables will be documented and summarized for all randomized subjects enrolled in the study who received at least one injection of IC2000 or Blue dye. Safety variables will include all adverse events (AEs) and adverse device effects (ADEs), concomitant medications, and vital signs. Safety analysis will be performed on all subjects who receive IC2000 regardless of whether LN mapping was initiated or successful.

Adverse events will be coded using the National Cancer Institute Common Terminology Criteria for Adverse Events (NCI CTCAE). Treatment-emergent AEs and ADEs will be summarized descriptively. The number and percentage of subjects experiencing AEs and ADEs and the total number of AEs and ADEs will be summarized by system organ class and preferred term. Associated AEs that investigators suspect are related to study treatment will also be summarized. Summary of each type of event will be prepared by severity and for all severities combined.

